**Year 2: Arms 4a/4b (1-4 years of age)**

Arms 2a/2b (5-8 year olds)		Months	13.5		14		15		16		17		18		19		20	23	26
		Visits	29	30	31	32	33	34	35	36	37	38	39	40	41	42	43	44	45
Procedures	Blood Volume	Study Day	378 (Rescreening)	385	392	406	420	434	448	462	476	490	504	518	532	546	560	644	728
		Days Post Vac	322	329	336/0	14	28	42	56	70	84	98	112	126	140	154	168	252	336
		Visit Windows (days) (1)	±84	±14	±112	±14	±14	±14	±14	±14	±14	±14	±14	±14	±14	±14	±14	±14	±56
Clinical Procedures																			
Updated medical history/ physical			X																
Reconsent			X																
Interim clinical evaluation				X	X	X	X	X	X	X	X	X	X	X	X	X	X	X	X
AE/SAE assessment			X	X	X	X	X	X	X	X	X	X	X	X	X	X	X	X	X
Conmed review			X	X	X	X	X	X	X	X	X	X	X	X	X	X	X	X	X
Artemether/Lumefantrine				X															
Unblinding (VU)																	X		
Laboratory Procedures																			
Malaria Blood Smear	CAP/EDTA		0.5	0.5	0.5	0.5	0.5	0.5	0.5	0.5	0.5	0.5	0.5	0.5	0.5	0.5	0.5	0.5	0.5
Malaria PCR/Genotyping/ Gametocyte	CAP/EDTA		0.5	0.5	0.5	0.5	0.5	0.5	0.5	0.5	0.5	0.5	0.5	0.5	0.5	0.5	0.5	0.5	0.5
Daily blood draw volume in mL			1	1	1	1	1	1	1	1	1	1	1	1	1	1	1	1	1
Cumulative blood volume in mL			150.5	151.5	152.5	153.5	154.5	155.5	156.5	157.5	158.5	159.5	160.5	161.5	162.5	163.5	164.5	165.5	166.5
1 Visit windows are based off timing of days post the preceding vaccination; broad visit window in place for Booster dose in attempt to group VU together and provide flexibility given the ongoing COVID pandemic; increased visit windows for visits to align with parental visits																			

**Year 2: Arms 2a/2b (5-8 years of age; Pilot Phase)**

Arms 2a/2b (5-8 year olds)		Months	15.5		16				17		18		19		20		21		22	25	28
		Visits	32	33	34	35	36	37	38	39	40	41	42	43	44	45	46	47	48	49	50
Procedures	Blood Volume	Study Day	434 (Rescreening)	441	448	451	455	462	476	490	504	518	532	546	560	574	588	602	616	700	784
		Days Post Vac	322	329	336/0	3	7	14	28	42	56	70	84	98	112	126	140	154	168	252	336
		Visit Windows (days) (1)	±84	±7	±112	±1	±2	±7	±7	±7	±7	±7	±7	±7	±7	±7	±7	±7	±7	±7	±56
Clinical Procedures																					
Updated medical history/ physical			X																		
Reconsent			X																		
Pre-test/Post-test HIV counseling			X																		
Interim clinical evaluation				X	X	X	X	X	X	X	X	X	X	X	X	X	X	X	X	X	X
AE/SAE assessment			X	X	X	X	X	X	X	X	X	X	X	X	X	X	X	X	X	X	X
Conmed review			X	X	X	X	X	X	X	X	X	X	X	X	X	X	X	X	X	X	X
Artemether/Lumefantrine				X																	
VACCINATION					X																
Unblinding																				X	
Laboratory Procedures																					
CBC with differential	EDTA		2		2	2		2													
ALT/ Creatinine	SST		5		3	3		3													
HIV testing	SST																				
Malaria Blood Smear	CAP/EDTA		0.5		0.5			0.5	0.5	0.5	0.5	0.5	0.5	0.5	0.5	0.5	0.5	0.5	0.5	0.5	0.5
Malaria PCR/Genotyping/ Gametocyte	CAP/EDTA		0.5		0.5			0.5	0.5	0.5	0.5	0.5	0.5	0.5	0.5	0.5	0.5	0.5	0.5	0.5	0.5
Pfs230 ELISA	SST				5			5			5			5					5	5	5
SMFA (3)																					
Transcriptional Analysis	PaxGene		1			1		1												1	
Daily blood draw volume in mL			9	0	11	6	0	11	1	1	6	1	1	1	6	1	1	1	7	6	6
Cumulative blood volume in mL			170	170	181	187	187	198	199	200	206	207	208	209	215	216	217	218	225	231	237
1 Visit windows are based off timing of days post the preceding vaccination; broad visit window in place for Booster dose in attempt to group VU together and provide flexibility given the ongoing COVID pandemic 2 SMFA may be completed on subjects at Study Day 448 and 504; other SMFA time points indicated above will be completed depending on associated ELISA results at that time point.																					

**Year 2: Arms 3a/3b (5-8 years of age; Main Phase)**

Arms 3a/3b (5-8 year olds)		Months	13.5		14				15		16		17		18		19		20	23	26
		Visits	29	30	31	32	33	34	35	36	37	38	39	40	41	42	43	44	45	46	47
Procedures	Blood Volume	Study Day	378 (Rescreening)	385	392	395	399	406	420	434	448	462	476	490	504	518	532	546	560	644	728
		Days Post Vac	322	329	336/0	3	7	14	28	42	56	70	84	98	112	126	140	154	168	252	336
		Visit Windows (days) (1)	±84	±7	±112	±1	±2	±7	±7	±7	±7	±7	±7	±7	±7	±7	±7	±7	±7	±7	±56
Clinical Procedures																					
Updated medical history/ physical			X																		
Reconsent			X																		
Pre-test/Post-test HIV counseling			X																		
Interim clinical evaluation				X	X	X	X	X	X	X	X	X	X	X	X	X	X	X	X	X	X
AE/SAE assessment			X	X	X	X	X	X	X	X	X	X	X	X	X	X	X	X	X	X	X
Commed review			X	X	X	X	X	X	X	X	X	X	X	X	X	X	X	X	X	X	X
Artemether/Lumefantrine				X																	
VACCINATION					X																
Unblinding																				X	
Laboratory Procedures																					
CBC with differential	EDTA		2		2	2		2													
ALT/ Creatinine	SST		5		3	3		3													
HIV testing	SST																				
Malaria Blood Smear	CAP/EDTA		0.5		0.5			0.5	0.5	0.5	0.5	0.5	0.5	0.5	0.5	0.5	0.5	0.5	0.5	0.5	0.5
Malaria PCR/Genotyping/ Gametocyte	CAP/EDTA		0.5		0.5			0.5	0.5	0.5	0.5	0.5	0.5	0.5	0.5	0.5	0.5	0.5	0.5	0.5	0.5
Pfs230 ELISA	SST				5			5			5				5				5	5	5
SMFA (3)																					
Transcriptional Analysis	PaxGene		1			1		1												1	
Daily blood draw volume in mL			9	0	11	6	0	11	1	1	6	1	1	1	6	1	1	1	7	6	6
Cumulative blood volume in mL			158.5	158.5	169.5	175.5	175.5	186.5	187.5	188.5	194.5	195.5	196.5	197.5	203.5	204.5	205.5	206.5	213.5	219.5	225.5
1 Visit windows are based off timing of days post the preceding vaccination; broad visit window in place for Booster dose in attempt to group VU together and provide flexibility given the ongoing COVID pandemic																					
2 SMFA may be completed on subjects at Study Day 336 and 448; other SMFA time points indicated above will be completed depending on associated ELISA results at that time point.																					

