### Comparator Vaccines

**HAVRIX:** inactivated hepatitis A viral vaccine adsorbed on aluminum hydroxide. HAVRIX is indicated for active immunization against disease caused by hepatitis A virus (HAV). HAVRIX is approved for use in persons 12 months of age and older with 2 doses (0, 6 months). Dosed on days 0 and 392/448.

**TYPHIM Vi:** polysaccharide vaccine containing the cell surface Vi polysaccharide extracted from *Salmonella enterica serovar Typhi*, *S typhi* Ty2 strains; non-adjuvanted. TYPHIM Vi is indicated for active immunization against typhoid fever in subjects

2 years of age and over and is given as a single dose. Dosed on day 28.

**Menactra®** (meningococcal serogroup A, C, Y, and W-135): is a sterile, intramuscularly administered vaccine that contains *Neisseria meningitidis* serogroup A, C, Y, and W-135 capsular polysaccharide antigens individually conjugated to diphtheria toxoid protein. A single dose (0.5 mL) is recommended for those individuals 2 years of age and older who are otherwise healthy and are at increased risk for meningococcal disease (e.g., individuals in an epidemic or highly endemic country such as Mali).

Sample Size:	N~1960 (approximately 137 family compounds/vaccine units) N=60 (pilot) N~1500 (main, vaccine) N~400 (main, no vaccine)
Accrual Ceiling:	N=2380 N=80 (pilot) N=1800 (main, vaccine) N=500 (main, no vaccine)
Accrual Period:	March 2019-September 2019 (primary series) June 2020-October 2020 (4 th vaccination; continuation on study)
Study Duration:	Start Date: Approximately March 2019 End Date: Approximately October 2021  Study participants will be enrolled for a total of approximately 26 to 28 months (for up to 12 months following the last vaccination) depending on vaccination schedule and arm assignment and timing of screening
Study Population:	Pilot: Malian children 5-18 years of age Main (vaccine): Malians 5 years of age and older Main (no vaccine): Malian children 1-4 years of age
Study Design:	Two phase study: pilot, main  Pilot Age de-escalating, double-blind, randomized comparator controlled; pilot groups will join main at the time of vaccine #3 Group 1: 9 to 18 years of age (n=30)

- **Arm 1a** (n=15), to receive 40 µg of Pfs230D1M-EPA/AS01 on days 0, 28, 126, 448; receipt of artemether/lumefantrine (AL) on day -7

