window when within-household transmission may be maximal; 2) block parasite transmission during the time window when the frequency of positive DSF may be maximal. By changing the dosing schedule so that the second dose of vaccine is given early August and the third dose of the vaccine is given in early September 2019, we expect to induce high transmission reducing and blocking activities during peak transmission season, which will maximize the impact of the vaccine on parasite circulation within households *in natura* and on parasite transmission in the DSF assay. Indeed, as mentioned in the **Section 3.2.2** of the study protocol, preliminary findings of a pilot vaccine trial indicate that Pfs230D1M-EPA/AS01 transmission reducing activity, as measured in standard membrane feeding assays, is statistically significantly higher 3 months after the 3rd dose compared to 3 months after the 2nd dose. Hence, giving the third vaccine dose one month rather than 5 months after the second dose will allow us to maximize antibody titers (and we therefore expect serum functional activity) during the periods of maximal intra-household transmission and of most frequent DSF transmission events.

These two factors, the expected relative increase in within-randomization unit parasite circulation during the rainy season and the proportionally high number of human-to-mosquito transmission events in the same period, implies that by administering a third dose of the Pfs230D1M-EPA/AS01 vaccine on study day 56 rather than on day 168, transmission blocking antibody levels will be sustainably high when the effect of the vaccine on prospective risk of human malaria infection would provide maximal benefit to the vaccinated units.

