**Table 7. Summary of Study Progress for 19-I-N086**

	Pilot Phase		Main Phase			
	Arm 2a/2b 5-8 yo	Arm 1a/1b 9-18 yo	Arm 3a/3b 5-8 yo	Arm 3c/3d 9-18 yo	Arm 3e/3f ≥19 yo	Arm 4a/4b 1-4 yo
Number subjects enrolled	30	30	185	369	495	192
Timing of enrollment	May 2019	Apr 2019	Jun to Sep 2019			Aug to Nov 2019
Number subjects received ≥1 vaccine	30	30	183	368	490	--
Timing of vaccination	May to Oct 2019	Apr to Sep 2019	Jun to Nov 2019			--
Number subjects AL dosed prior to Vax #3	29	--	181	--	--	--
Timing of AL dosing prior to Vax #3	Aug to Oct 2019	--	Aug to Nov 2019	--	--	--
Number subjects underwent DSF ≥1	--	26	--	358	--	--
Timing of start -end of DSFs	--	Sep to Dec 2019	--	Sep 2019 to Mar 2020	--	--

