## 7 Study Design

### 7.1 Description of the Study Design

This is a Phase 2, double-blind, block (compound/vaccine unit)-randomized, comparator-controlled study designed to evaluate the safety, reactogenicity, immunogenicity, transmission-blocking activity, and subsequent vaccine efficacy of Pfs230D1M conjugate formulated on AS01. Subjects will be drawn from approximately 137 compounds/vaccine units (extended families/neighboring compounds) in Doneguebougou and surrounding villages that have agreed as a family/compound to participate in the study. Individuals within the compound will not be randomized to individual arm assignments, but rather an entire family/compound will be randomized as a whole to receive either Pfs230D1M-EPA/AS01 or comparator vaccine in eligible and willing residents in that family/compound (vaccine unit) as well as the enrolled young children (1-4 years of age) in the parasitemia cohort (Group 4).

As previously noted, all eligible and enrolled pilot and main phase subjects  $\geq 5$  years of age or older will receive AL treatment prior to first vaccination as well as either Pfs230D1M-EPA/AS01 or comparator vaccine at 0, 28, 56, and 392 days (main phase) and 0, 28, 126, and 448 days (pilot phase). All vaccinated subjects will be followed for safety and tolerability, as well as immunogenicity via ELISA and functional antibody responses via SMFA.

Subjects 5-8 years of age will also receive AL treatment  $\sim 14$  days prior to vaccination #3 and  $\sim 7$  days prior to vaccination #4 in their compound, regardless of other antimalarial treatments

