administered prior, subject to clinician's discretion. Children 1-4 years of age will be enrolled just before the malaria transmission season and will receive AL concomitantly with children 5-8 years of age who will be treated ~14 days before the 3rd vaccine dose and ~7 days prior to vaccination #4. All enrolled subjects (except adults,  $\geq 19$  years old) will be monitored for patent parasitemia every 2 weeks, and all enrolled subjects during unscheduled visits if clinically indicated, for at least 6 months up to 12 months post vaccination, with time to patent parasitemia being evaluated as a vaccine efficacy timepoint in children 1-8 years of age as well as 9-18 years of age within the compounds (separate secondary evaluation given expected nighttime mobility and no pre-transmission season AL treatment). Preteen and adolescent subjects will also be assessed by DSF for vaccine activity starting 2 weeks post receipt of vaccination #3 and post receipt of vaccination #4; DSFs will be completed every 2 weeks for a total of 8 DSF (post vaccination #3) and for a total of 10 DSF (post vaccination #4).

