**Figure 28. Fourth Dose (Year 2) Study Schema**

Updated study schedule for fourth dose. Pilot and Main Phase will align with their VUs for timing of AL dosing and vaccination.

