Malaria Blood Smear	CAP/EDTA		0.5	0.5			0.5	0.5				0.5	0.5				0.5	0.5	0.5	0.5	0.5	0.5	0.5	0.5	0.5	0.5	0.5	0.5	0.5	0.5	0.5	0.5
Malaria PCR/Genotyping/ Gametocyte	CAP/EDTA		1	1			1	1				1	1				1	1	1	1	1	1	1	1	1	1	1	1	1	1	1	1
Pf230 ELISA	SST			10			5	5				5	5				5			5										5		5
SMFA (3)																																
Transcriptional Analysis	PaxGene		1	1		1					1						1														1	
Daily blood draw volume in mL			10	7.5	17.5	0	6	0	11.5	11.5	0	6	0	11.5	11.5	0	6	0	11.5	1.5	1.5	6.5	1.5	1.5	1.5	1.5	6.5	1.5	1.5	1.5	7.5	6.5
Cumulative blood volume in mL			10	17.5	35	35	41	41	52.5	64	64	70	70	81.5	93	93	99	99	110.5	112	113.5	120	121.5	123	124.5	131	132.5	134	135.5	143	149.5	
1 Visit windows are based off timing of days post the preceding vaccination																																
2 Hemoglobin typing, if not completed at screening, given completed retrospectively, can be completed at any time when there's a scheduled blood draw with an EDTA tube																																
3 SMFA may be completed on subjects at Study Day 0 and 182; other SMFA time points indicated above will be completed depending on associated ELISA results at that time point.																																
4 Note this visit may occur twice depending on the approval of the V3.0 protocol; the first D42 visit (D42A) will include all D42 procedures EXCEPT AL dosing. This visit will occur to maintain safety labs and assessments are completed on ALL subjects approximately 14 days post Vaccination #2 (±3 days). If this visit occurs, the next visit will be D42B for AL dosing and completed of ALL procedures as outlined in the visit (if D42A completed >14 days from D42B). This is to ensure the AL dosing in participants occurs approximately 14 days prior to Vaccination #3. If both visits are completed, subjects will receive an additional 3000 CFA (\$6 USD).																																

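### The Year 2 AL visit is not windowed from dose 4, so the stated 7-day interval and the AL window can conflict; Appendix B also carries a stray Day 378 AL course for 1-4 year olds

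*Combined protocol and SAP*

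**What the plan says.** **Interval.** For 5-8 year olds, Section 7.1 places the Year 2 AL course about 7 "days prior to vaccination #4 in their compound, regardless of other antimalarial treatments", and then leaves room for clinician discretion. The 1-4 year olds are dosed together with the 5-8s, who are to be "treated ~14 days before the 3rd vaccine dose and ~7 days prior to vaccination #4". The nominal days agree: AL on Day 385 and dose 4 on Day 392 (main), and Days 441 and 448 (pilot).

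**Windows.** The footnote to the Year 2 tables in Appendix A reads "Visit windows are based off timing of days post the preceding vaccination; broad visit window in place for Booster dose". It goes on to give the reasons: keeping units together and flexibility during the pandemic. For both the AL visit and the dose 4 visit, the preceding vaccination is dose 3. The windows are AL ±7 days for Arms 2a/2b and 3a/3b, AL ±14 days for Arms 4a/4b, and dose 4 ±112 days.

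**Alignment.** The caption of Figure 28 says "Pilot and Main Phase will align with their VUs for timing of AL dosing and vaccination". The footnote for Arms 4a/4b adds that their windows were widened to match parental visits. Neither gives an interval.

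**Year 1.** Note 4 to the Year 1 table for Arms 3a/3b gives its purpose: "This is to ensure the AL dosing in participants occurs approximately 14 days prior to Vaccination #3". A note to the Year 1 table for Arms 4a/4b ties their AL visit to the unit's visit 14 days before dose 3.

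**AL days for 1-4s.** The Protocol Summary and Section 7.2.2 list AL on Days -14 and 385 only, and the Year 2 table in Appendix A marks Day 385 only. Appendix B, Arms 4a/4b, orders a first AL dose at Study Day 378, with further doses on days -13 and -12, and then a full course on Days 385-387.

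**The concern.** Two visits that should be a week apart are windowed independently from a third event about eleven months earlier, and one window is far wider than the other. If a unit's dose 4 moves well away from Day 392, the AL window does not move with it. A site then either keeps the Section 7.1 interval and logs an out-of-window AL visit, or keeps the AL window and loses the interval.

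AL clears existing infection before smear follow-up in 1-8 year olds, and Section 17.3.2.2 bases power in that group on the risk of first infection. If AL came long before dose 4, infections acquired in between could appear as positives after dose 4 and dilute the secondary efficacy comparison.

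The Day 378 order is a dosing instruction. Followed literally, it gives continuing 1-4 year olds an unplanned three-day AL course a nominal 7 days before the planned one.

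**Working it through.** **Stated interval.** 392 − 385 = 7 days (main) and 448 − 441 = 7 days (pilot). The nominal schedule reproduces Section 7.1.

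**Year 2 windows.** The inputs are the Year 2 tables in Appendix A. The maximum lead is the last permitted dose 4 day minus the first permitted AL day. AL exactly 7 days before dose 4 is in window when dose 4 lies between the first AL day + 7 and the last AL day + 7.

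| Arms | AL window | Dose 4 window | Largest in-window lead | Dose 4 days with AL exactly 7 days earlier in window |
|---|---|---|---|---|
| 3a/3b | 378-392 | 280-504 | 504 − 378 = 126 | 385-399: 15 of 225 |
| 2a/2b (pilot) | 434-448 | 336-560 | 560 − 434 = 126 | 441-455: 15 of 225 |
| 4a/4b | 371-399 | 280-504 (unit's dose 4) | 504 − 371 = 133 | 378-406: 29 of 225 |

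If a lead of 0 to 14 days is accepted as about 7, the last column becomes 378-406 (29 days) for Arms 3a/3b and 371-413 (43 days) for Arms 4a/4b. If dose 4 falls before Day 378 (5-8s) or Day 371 (1-4s), no in-window AL day precedes it: 378 − 280 = 98 and 371 − 280 = 91 of the 225 permitted days. These counts treat every permitted day alike. They describe the rule, not how many units were affected.

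**Calendar limit.** The Protocol Summary gives "June 2020-October 2020" for the fourth vaccination. Assume dose 4 ended on 31 October 2020. The earliest in-window AL day is 329 − 7 = 322 days after dose 3 (5-8s) or 329 − 14 = 315 days (1-4s). Section 1.2.3.1.1.2 plans that "the third dose of the vaccine is given in early September 2019", and Table 7 gives "Jun to Nov 2019" for main-phase vaccinations, so a range of dose 3 dates is shown.

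| Dose 3 date (2019) | Earliest AL, 5-8s | Largest lead, 5-8s | Largest lead, 1-4s |
|---|---|---|---|
| 1 September | 19 July 2020 | 104 days | 111 days |
| 1 October | 18 August 2020 | 74 days | 81 days |
| 1 November | 18 September 2020 | 43 days | 50 days |
| 30 November | 17 October 2020 | 14 days | 21 days |

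**Year 1 for comparison.** Appendix B gives AL on Day 42 ± 28 (14-70) and dose 3 on Day 56 ± 56 (0-112). The largest lead was 112 − 14 = 98 days, so the structure was the same. What Year 1 had in addition was the written tie in the notes for main-phase 5-8s and for 1-4s.

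**AL courses in 1-4s.** Planned: Days -14 and 385, two courses. With the Day 378 line: three. Days -13 and -12 are the follow-on days of the Year 1 Day -14 visit in the same part of Appendix B, so the line was evidently carried over from there.

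**After the fix.** With AL windowed at dose 4 minus 7 days, the lead is 0 to 14 days at ±7, or 4 to 10 days at ±3, wherever dose 4 falls.

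**The case against.** The strongest defence is that the windows should be read together with the text. A site following Section 7.1 would book AL a week before dose 4, and the Figure 28 caption and the Arms 4a/4b footnote point the same way. That stands: the leads of up to 126 and 133 days arise only if Section 7.1 is ignored. A reader might infer that the plan intends or tolerates AL four months before dose 4, and the documents do not support that. What remains is that a site following Section 7.1 can be forced out of window.

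A reader might also infer that Year 2 dropped a protection that the Year 1 windows provided. It did not, because the Year 1 windows were also counted from the preceding vaccination. Only the explanatory notes were lost, and the Year 1 pilot 5-8 table had none.

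The Précis gives a second aim for Year 2 AL, treatment before the transmission season, which could justify a narrow AL window. This carries limited weight. For dose 3 on 1 September 2019, nominal AL (329 days later) is 26 July 2020, already inside the June-December season described in Section 9.1.

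On harm, there is real mitigation. The dose 4 visit has its own smear and PCR, 1-4s also have both at the Day 385 visit, symptomatic malaria is treated (Section 12.5.1.1), and under-5s receive seasonal chemoprevention (Section 1.2.4). Section 17.2.2 compares rates of positive smears and does not say that the Year 2 risk period starts at dose 4.

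On Day 378, the follow-on days cannot be carried out, and three other places list Day 385 only. A reader might infer that all 192 enrolled 1-4 year olds would receive an extra course. That assumes sites act on an instruction that is visibly a copying error.

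**Conclusion.** Wrong as written, and minor. The Year 2 windows do not carry the interval that Section 7.1 sets. When dose 4 falls outside Day 385-399 (5-8s) or 378-406 (1-4s), AL exactly 7 days before it is out of window. The Day 378 AL order in Appendix B conflicts with the Protocol Summary, Section 7.2.2 and Appendix A.

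The arithmetic is certain; the consequence is not. The documents do not say how many units had dose 4 far from Day 392 or what the actual intervals were, so the effect on the smear endpoint in 1-8s cannot be sized and may be small. It would be dilution. A reader might infer bias between arms, but whole units are randomized and blinded, and nothing suggests that timing would differ by arm. The primary DSF endpoint is unaffected, because 9-18 year olds receive no AL before dose 4.

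Three clerical slips lie nearby and add no weight. The pilot AL visit is 441 − 126 = 315 days after dose 3 in Appendix B but 329 in Appendix A. The Day 441/385 AL visit in Appendix B is labelled as the day of dose 4. Section 18.4.2 gives one or two AL courses per subject, although 5-8s are scheduled for three.

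**What to change.** 1. In the Year 2 schedules for Arms 2a/2b, 3a/3b and 4a/4b (Appendices A and B), add a footnote that the AL visit is windowed from the vaccine unit's scheduled dose 4 date: 7 days before it, with a tolerance between ±3 and ±7 days. AL then moves with dose 4. Keep the ±112-day dose 4 window.
2. In Appendix B, Arms 4a/4b, delete the AL order and its follow-on doses at Study Day 378. The Day 385-387 course stays.
3. Correct the three clerical slips in the same edit.

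The cost is a few table and footnote edits, a site memo, and slightly less freedom in booking AL visits. If dose 4 slips after AL has been given, the clinician discretion already in Section 7.1 still applies.
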